#### 11.3.2 Per Protocol Population

Children who receive 70% of the prescribed doses of study product (whether antibiotics or placebo) will comprise the per protocol population. This population will form the basis of secondary, supportive analyses of the efficacy and safety endpoints.

### 11.4 Efficacy Assessments

The daily PRSS score over the first 10 days of therapy (Day 1 to 11) will be recorded by parents/legal guardians using an electronic tablet or a personal computer, a cell phone, or a tablet every evening. A routine end-of-study follow-up clinic visit will be held once during Days 12 to 18 day. An interim visit will be scheduled if the PRSS score has not improved as expected, i.e. if child meets definition for treatment failure.

#### **11.4.1 Primary Efficacy Variable**

The PRSS score over the 10 days of therapy will serve as the primary efficacy variable because it represents the outcome that it is clinically most relevant. Clinicians prescribe antimicrobials for children with acute sinusitis under the assumption that it hastens the resolution of symptoms. Thus, to assess the degree of improvement and/or deterioration we chose a validated symptom score to serve as the primary efficacy variable.

The PRSS (See Supplement B) consists of eight discrete items: runny nose, stuffy nose, daytime cough, nighttime cough, sleeping difficulty, trouble breathing through the nose, irritability, and being tired. Parents/legal guardians are asked to rate these symptoms, as “none”, “almost none”, “a little”, “some”, “a lot”, or “an extreme amount” with corresponding scores of 0 to 5. PRSS scores may thus range from 0 to 40.

#### **11.4.2 Secondary Efficacy Variables**

The secondary efficacy variables include:

- 1) Treatment failure - Children who are not improving at the expected rate will be identified through daily monitoring of the PRSS scores by the study staff. These children will be seen by the study team and rescue medication will be prescribed, as clinically indicated. We will define treatment failure if any of the following conditions are met:
  - a. Worsening at any time—total PRSS score increased by >20% from entry.
  - b. No change by 48 hours—total PRSS score decreased by <2 points from entry (Day 1) to Day 3.
  - c. Failure to improve significantly by 72 hours—total PRSS score decreased by <20% from entry (Day 1) to Day 4.
  - d. PRSS decreased by <20% from enrollment on 2 consecutive occasions on Days 5-11
  - e. Still symptomatic (total PRSS score  $\geq$ 50% of entry score) at the time of the end-of-study follow-up visit (Days 12 to 18).
- 2) Development of AOM (acute symptoms and a bulging tympanic membrane) on Days 1 to 11.
- 3) Receipt of an antibiotic (other than the assigned study product) for any indication on Days 1 to 11.

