An end-of-study follow-up clinic visit will be held once during Days 12 to 18. If the parent/legal guardian is unable or unwilling to return for the end-of-study follow-up visit, we will offer to visit the patient's home.

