## 7 STUDY SCHEDULE

See Supplement A for the Schedule of Events table.

### 7.1 Screening – Day 1

Parents/legal guardians of children presenting to a participating center with URI symptoms will be introduced to study staff by office personnel. The research staff will question the parent regarding the presence and characteristics of their child's symptoms [duration of symptoms, course of symptoms (e.g., improving, staying the same, worsening), severity of symptoms (PRSS), history of allergic rhinitis, history of asthma]. If the provider's clinical assessment does not then reveal another etiology that would exclude the child from participating (e.g., AOM, pneumonia, streptococcal pharyngitis, wheezing) informed consent will be sought from the parent/legal guardian. We will attempt to enroll consecutive children meeting eligibility criteria. We will maintain logs of eligible children who are not enrolled.

### 7.2 Enrollment/Baseline Visit (Entry Visit) – Day 1

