## **7.5 Unscheduled Visit (Interim (Sick) Visit)**

If a child's PRSS score is not improving as expected, or if a parent is concerned about their child, an interim evaluation will be scheduled, usually on the same day. If the parent/legal guardian is unable to come to the office, a home visit may be offered. If the child cannot be seen and assessment of the child's symptoms by phone indicate that the child is not acutely worsening and no new symptoms are reported, an antibiotic may be started without an evaluation. A study team member will be available 24 hours/day, 7 days/week via cellular phone. Children failing study product will be treated with clindamycin plus cefixime, amoxicillin-clavulanate potassium, levofloxacin, or a similar antibiotic, as clinically indicated and without breaking the blind. The results of the nasopharyngeal culture may be used to guide therapy. The following procedures may be performed at this visit: interim medical history including visits to other health care providers and concomitant medications collection, temperature measurement, face/nose assessment, PRSS score, and adverse events monitoring. Temperature will be measured using appropriate method according to the child's age and parental preference (oral, rectal, axially, temporal, or tympanic).

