## 8 STUDY PROCEDURES/EVALUATIONS

### 8.1 Clinical Evaluations

**Medical History:** Will be obtained by interview of the parents/legal guardians. Parents/legal guardians will be queried regarding demographic characteristics, risk factors (day care attendance, exposure to smokers in the house), symptoms (type and duration, including some symptoms not included on the PRSS), and past medical history since birth (sinusitis, allergic rhinitis, asthma, and medications used to treat these) at the baseline visit. We will also ask parents/legal guardians to assess the severity of their child's symptoms using a visual analog scale anchored at "very mild" and "very severe". At the final end-of-study follow-up visit, we will ask parents to complete the PRSS, to answer question about visits to other providers, missed work, quality of life, and the need to make alternate daycare arrangements, and about adverse events.

**Medication History:** Will be obtained by interview of the parents/legal guardians. We will ask about previous antihistamines, decongestant, albuterol, or corticosteroid use during the past 7 days and antibiotics use up to 3 months before enrollment. We also track the use of these same medications along with analgesic medication through the end-of-study follow-up visit or early termination, whichever occurs first. Receipt of a systemic antibiotic while taking study medication will be recorded as this constitutes a secondary endpoint of the study. The use of these medications will be ascertained by parent/legal guardian interview at the end-of-study follow-up visit or early termination, whichever occurs first.

**Vital Signs:** Temperature and weight will be measured at enrollment/baseline visit and the interim (sick) visit (if not already taken for clinical care). Temperature will be measured using appropriate method according to the child's age and parental preference (oral, rectal, axially, temporal, or tympanic).

**Limited assessment of face and nose:** At the baseline and unscheduled interim (sick) visit, a targeted assessment of the face and nose using standardized methods will be performed by appropriate study personnel.

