## 18 SUPPLEMENTS

### 18.1 Supplement A: Schedule of Events

Study Procedure	Screening/ Enrollment/ Baseline/Entry Visit (Day 1)	Follow-up eVisits (Days 2-11*)	Unscheduled/ Interim (Sick) Visit	Final End-of- Study Follow-up Visit (Days 12-18)
Informed Consent	X			
Randomization	X			
Study Product Administration	X	X		
Medical History	X		X	X
Assessment of Face/Nose	X		X	
PRSS Score	X	X	X	X
Nasopharyngeal Swab (or Mid-Turbinate) obtained when possible	X			X
Adherence Assessment		X		
Concomitant Medications	X		X	X
Monitoring of Adverse Events	X	X	X	X
Collect Unused Study Product				X

\*Data collected using an electronic diary. Parents/legal guardians of subjects with missing diaries will be called.

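### The AOM endpoint needs an eardrum finding on Days 1–11, but no follow-up ear examination is listed; detection depends partly on symptom failure and could differ by arm if treatment changes it

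*Combined protocol and SAP*

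**What the plan says.** Sections 3.2.2 and 11.4.2 list the endpoint as "Development of AOM (acute symptoms and a bulging tympanic membrane) on Days 1 to 11". Section 11.7.3 compares it between arms with a Cochran-Mantel-Haenszel test stratified by site on the ITT set, and adds logistic regression on baseline and prognostic covariates.

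The examinations and contacts in the plan are these:

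- **Entry (7.1, Table 3).** AOM is an exclusion, applied through the provider's clinical assessment.
- **Days 2–11 (7.3, Supplement A).** Scheduled contacts are electronic diaries, with calls or texts for missing entries.
- **Unscheduled visit (7.5).** It is arranged when the PRSS is not improving as expected or when a parent is concerned. Beyond history and concomitant medications, the procedures that may be done are "temperature measurement, face/nose assessment, PRSS score, and adverse events monitoring". Section 8.1 says that at baseline and at this visit "a targeted assessment of the face and nose using standardized methods will be performed by appropriate study personnel".
- **Final visit (4, 7.4).** "An end-of-study follow-up clinic visit will be held once during Days 12 to 18", after the AOM window has closed. The row "Assessment of Face/Nose" in Supplement A is not marked for it.
- **Start of an antibiotic by phone (7.5).** If the child cannot be seen, "an antibiotic may be started without an evaluation", provided that the phone assessment shows no acute deterioration and nothing new.

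**The concern.** The definition turns on something seen through an otoscope. Section 2.2.2.1 itself describes AOM as a diagnosis made by looking directly at the ear. AOM is ruled out at entry, so an endpoint event needs a later ear examination, and the plan neither schedules nor lists one.

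Whether a child is examined in the window then depends partly on PRSS failure, which is what the antibiotic is meant to change. If it does so, the arms could differ in how often ears are looked at, and a difference in recorded AOM could be read as prevention of AOM. The site-stratified test does not address this. Nor does logistic regression on baseline covariates, because being examined is a post-randomisation event.

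**Working it through.** **1. Is there another route to the finding?**

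- *Adverse events.* Section 9.1 tracks protocol-defined diarrhoea, generalised rash, bacterial resistance, severe events and serious events. Table 4 marks other mild and moderate events as not collected, so an ordinary AOM would not be captured here.
- *Outside providers.* Visits elsewhere are asked about at the final visit (7.4). Sections 12 and 15.2 seek records to document another antibiotic. No text requires an outside diagnosis to meet the bulging-membrane definition.
- *Diary.* None of the eight PRSS items concerns the ear (11.4.1, Supplement B).

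This leaves unscheduled visits and outside providers.

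**2. How are unexamined children handled?** Section 11.8 gives worst-case and best-case analyses for missing dichotomous outcomes. It does not say whether a child whose ears were never examined is missing or AOM-negative.

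**3. How large could a distortion be?** The plan states no AOM rate, placebo failure rate or AOM power, so there is no figure to reproduce. What follows is an illustration.

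From the documents: about 344 children per arm (section 4), about 15% failure on antibiotic (3.2.2), two-sided 0.05 (11.6.1).

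Assumed:
- the true AOM rate is equal in the two arms and independent of PRSS failure;
- placebo failure is 25%, 35% or 50%;
- AOM is detected in 90% of cases among failing children, and in 10%, 30% or 50% of cases among the others.

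Detected share of true AOM = failure × 0.90 + (1 − failure) × detection in others.

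Antibiotic arm:
- others 10%: 0.15 × 0.90 + 0.85 × 0.10 = 0.22
- others 30%: 0.135 + 0.255 = 0.39
- others 50%: 0.135 + 0.425 = 0.56

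Placebo arm, in the same order:
- 25% failure: 0.30, 0.45, 0.60
- 35% failure: 0.38, 0.51, 0.64
- 50% failure: 0.50, 0.60, 0.70

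The true rate cancels, so the spurious antibiotic/placebo risk ratio is the ratio of these shares:

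| Placebo failure | Others 10% | Others 30% | Others 50% |
|---|---|---|---|
| 25% | 0.73 | 0.87 | 0.93 |
| 35% | 0.58 | 0.76 | 0.88 |
| 50% | 0.44 | 0.65 | 0.80 |

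If placebo failure is also 15%, every ratio is 1.00. If detection is complete in both arms, the ratio is 1.00 whatever the failure rates.

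**4. Chance of a falsely significant result favouring antibiotic** (nominal 2.5% in that tail), for an assumed true AOM rate of 5% / 10%:

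| Placebo failure | Others 10% | Others 30% | Others 50% |
|---|---|---|---|
| 25% | 6.7% / 9.7% | 4.6% / 5.8% | 3.6% / 4.1% |
| 35% | 13.6% / 23.2% | 7.6% / 11.5% | 4.9% / 6.4% |
| 50% | 28.1% / 50.4% | 14.1% / 24.5% | 7.6% / 11.4% |

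These use a two-proportion power calculation that ignores site strata. They are rough, because the counts are small. The largest entry compares 344 × 0.10 × 0.22 = 7.6 with 344 × 0.10 × 0.50 = 17.2 expected detected cases.

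**The case against.** Several stronger readings are tempting, and the documents do not support them.

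- *The arms are compared with unequal detection.* The triggers are masked and identical by arm. Detection differs only if treatment changes PRSS failure or parental concern.
- *AOM in a child whose nasal symptoms are improving leads to no visit.* Section 7.5 allows a visit on parental concern whatever the score, and study staff can be reached at all hours. The PRSS also scores irritability, sleep and tiredness, which an ear infection may raise. No document gives the share of visits prompted by the PRSS.
- *Only failing children are ever examined.* The ratio would then equal the ratio of failure rates, from 0.15/0.25 = 0.60 down to 0.15/0.50 = 0.30. The parent-prompted and outside routes rule out this limiting case as a description of the plan.
- *Failing children routinely get antibiotics with no examination.* The phone route is confined to children who cannot be seen, are not acutely worse and have nothing new to report.
- *Unexamined children are counted as AOM-free.* The text is silent.

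The schedule may also be an incomplete list of what clinicians do. It shows no ear examination at baseline either, although AOM is excluded there. The Manual of Procedures, not available here, might specify otoscopy. AOM cases have acute symptoms, so they are probably seen more readily than the independence assumption allows, which would shrink the distortion.

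All of this limits the size and certainty of the problem. What remains is that the protocol specifies no ear assessment that is independent of the symptom course for an endpoint that it tests between arms.

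**Conclusion.** The concern holds in conditional form. As written, AOM is ascertained through contacts that depend partly on PRSS failure. Under-detection is likely in both arms; bias between arms follows only if treatment alters PRSS failure or parental concern. In that case the recorded comparison would tend to favour the antibiotic even with no effect on AOM.

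The illustrative ratio of 0.44 to 0.93 rests on one protocol figure, the 15% failure on antibiotic; the other inputs are assumed. It shows direction and possible scale and is not an estimate. The matter is confined to one of three secondary efficacy variables and leaves the primary interaction tests untouched. It is worth correcting because the correction is cheap and a claim that treatment prevents AOM would otherwise be hard to defend.

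**What to change.** In 3.2.2, 11.4.2 and 11.7.3:

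1. Define the endpoint as clinically detected AOM, at an unscheduled study visit or by an outside provider, on Days 1–11.
2. List ear examination among the interim-visit assessments in 7.5, 8.1 and Supplement A, and record whether it was done and what was found. Record outside AOM diagnoses as well.
3. Report by arm the number of children whose ears were examined on Days 1–11.
4. Present the AOM comparison as descriptive, with no claim that treatment prevents AOM.

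Two alternatives are less useful. Coding every unexamined child as missing under 11.8 would leave little to analyse: if examinations followed failure alone, 85% of the antibiotic arm (1 − 0.15) and 50–75% of placebo (1 − 0.50 to 1 − 0.25) would be missing, and the bounds would be uninformative. Adding an ear examination on Days 12–18 would answer a different question, since it misses AOM that arose and cleared or was treated earlier.

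The cost is some wording, a small eCRF addition at visits already held, and an AOM result that is descriptive rather than confirmatory.

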### **11.5 Safety and Tolerability Assessments**

Safety and tolerability assessments include:

- 1) Adverse events - The proportions of children experiencing certain adverse events will be compared. We will also track the duration of these adverse events. Diarrhea will be

defined as the occurrence of  $\geq 3$  watery stools in 1 day or 2 watery stools per day for 2 consecutive days. This will be tracked in the daily diary. Changes in bacterial resistance from baseline to follow-up will be tabulated.

- 2) Compliance - In the daily diary, we will ask parents/legal guardians to record whether they administered the doses of study product. Administration of  $\geq 70\%$  of the doses will be considered compliant.

## 11.6 Statistical Analyses

### 11.6.1 General Considerations

Study data will be monitored on an ongoing basis by the Data Management and Statistical Unit in the Division of General Academic Pediatrics at the Children's Hospital of Pittsburgh. Final cleaning and editing of the study database will be carried out after the last patient completes follow-up. Unblinding of treatment assignments will not be performed until the study data are cleaned, queries resolved, and database lock achieved. All changes to the study database will be documented. A permanent archive of the database will be maintained by the DMSU.

A 2x2 factorial design, adjusted for multiple testing, will be used to detect interactions for the longitudinal outcome, where Factor A will be antibiotic-treated vs. placebo and Factor B will be either colored nasal discharge (yellow or green vs. clear) or nasopharyngeal colonization (positive vs. negative).

All statistical tests will be two-tailed and conducted at global significance level of 0.05. For the primary efficacy analysis, the significance level for the final analysis will take into account the interim analysis. Sites with few children randomized may be pooled. Pooling of study sites will occur prior to unblinding. All programs used in the statistical analysis will be documented, tested, and archived. Archiving of statistical analyses at the DMSU includes the original written specifications for the analyses, any subsequent modifications, the computer program file, and the log, list and other output files produced by the program. The DMSU will use the most current version of SAS®.

### 11.6.2 Interim Analysis

Interim analysis will occur after 344 children have completed this trial. Type I error will be controlled using the method of Fleming, Harrington and O'Brien and testing will be conducted at significance levels of 0.005 and 0.048 at the interim and final analyses, respectively. If at least one of the tests for interaction is significant (i.e., if there is unequivocal evidence of treatment effect heterogeneity), the DSMB may consider recommending stopping this trial early.

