## 11 STATISTICAL CONSIDERATIONS

### 11.1 Study Hypotheses

Hypothesis 1: Children not colonized with respiratory pathogens are unlikely to benefit from antimicrobial therapy.

Hypothesis 2: Children without colored nasal discharge are unlikely to benefit from antimicrobial therapy.

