### **11.7 Efficacy Analyses**

#### **11.7.1 Primary Efficacy Analysis of the Primary Efficacy Endpoint**

We present compelling preliminary data and extensive literature suggesting that the effect of antimicrobial therapy is likely to differ in certain subgroups of children with acute sinusitis. Accordingly, the primary efficacy analysis will assess the heterogeneity of treatment effect in subpopulations defined by presence of nasopharyngeal colonization and by the presence of colored nasal discharge (i.e., to test for interaction between treatment and subgroup effects).

Interactions between treatment group and each subgrouping variable will be tested simultaneously. A Generalized Estimating Equations (GEE) model will be fit by including treatment by subpopulation interaction terms (adjusted for the baseline PRSS score) using the ITT dataset (see Section 6.8 for detailed multiple testing procedure). The regression analysis will be adjusted for clinical site as a potential confounding factor.

Assumptions required for the validity of GEE will be assessed. These will include (i) the marginal mean of the response depends on a link function, (ii) the marginal variance depends on the marginal mean, and (iii) the correlation within subject depends on the marginal mean and other parameters. Therefore an appropriate link function will be chosen for the primary outcome and the goodness of fit of the model will be assessed.

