## 11.11 Sample Size Justification

To estimate the sample size for this trial, we used estimates of within-subject correlation and grand variance from our preliminary data of children diagnosed with acute sinusitis. Because two simultaneous tests for interactions are being conducted, we used a two-sided significance level of 0.025 (50:50 split of the overall significance level of 0.05 for Bonferroni adjustment).

Assuming an  $\alpha$  of 0.025 (two-sided test), 344 evaluable children per treatment group will provide statistical power of 80% to detect an interaction effect size of 2.5 points in the mean symptom score (as measured by the PRSS) over the 10-day period assuming, as per results presented in Leon and Heo, that the required sample size to detect an interaction between treatment group and a subgroup would be four times that of a main effect of the same magnitude for a repeated measures outcome under a 2x2 factorial design.

Even though we have calculated the sample size using the simple Bonferroni procedure, for the final analysis we will use a modified Bonferroni procedure for multiple testing, which is not as conservative for highly correlated test statistics. Under the Simes' procedure, the null hypothesis associated with the smallest p-value will be rejected if the p-value is smaller than or equal to  $\alpha / 2$  and one associated with the second smallest p-value will be rejected if the p-value is smaller than or equal to  $\alpha / 2$ . Here  $\alpha / 2$  is the appropriate significance level for the interim or definitive analysis. Specifically, the (ordered) observed p-values will be compared using 0.0025 and 0.005 for the interim analysis and using 0.024 and 0.048 for the definitive analysis.

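### If the trial stops at the interim look, the plan offers only the ordinary GEE estimate and interval for the interaction; a repeated confidence interval should be pre-specified

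*Combined protocol and SAP*

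**What the plan says.** Section 11.6.2 places one interim analysis after 344 children have completed the trial. It controls type I error with a group-sequential method at levels 0.005 (interim) and 0.048 (final). If at least one interaction test is significant, "the DSMB may consider recommending stopping this trial early".

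Section 11.11 splits these levels between the two interaction tests: "the (ordered) observed p-values will be compared using 0.0025 and 0.005 for the interim analysis".

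For estimation, section 11.7.1 states that "A Generalized Estimating Equations (GEE) model will be fit by including treatment by subpopulation interaction terms", adjusted for baseline PRSS and site. Sections 11.6.1, 11.6.2 and 11.11 carry the interim look into the significance levels and nowhere else. No section names an interval or estimate for a trial that stops early.

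The conclusion the trial is built to support is stated in section 11.1: "Children not colonized with respiratory pathogens are unlikely to benefit from antimicrobial therapy", with a parallel hypothesis for children without colored discharge.

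**The concern.** A test that crosses a strict boundary on half the data does so partly because its estimate came out high. Adjusting the significance level protects the decision to reject. It does not protect the size of the effect that is then reported, or the coverage of its interval.

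The direction matters here. An inflated interaction makes the treatment effect look too large in marker-positive children and too small in marker-negative children. When the true interaction lies in the hypothesised direction, the second error pushes toward the conclusion in section 11.1, so a modest real benefit could be read as none. If the true marker-negative effect is already zero, the same shift suggests harm.

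**Working it through.** **Inputs**

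- Section 11.11: "344 evaluable children per treatment group will provide statistical power of 80% to detect an interaction effect size of 2.5 points", and "we used a two-sided significance level of 0.025".
- Section 11.11: "we used estimates of within-subject correlation and grand variance from our preliminary data", but neither value is printed. The standard error (SE) must therefore be back-solved from the stated power.
- Section 11.6.2: interim at 344 of 688, taken as half the information.
- Section 11.11: first ordered interim threshold 0.0025, critical value 3.023.
- Section 2.1.3: 49% of cultured children carried pathogens. A 50:50 split is assumed for both markers.

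**1. The plan's own figures**

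SE at 688 = 2.5 / (2.2414 + 0.8416) = 0.811.

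Implied SD of a child's mean score = 0.811 × √688 / 4 = 5.32.

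Main-effect n per group = 2 × (3.083)² × 5.32² / 2.5² ≈ 86. Section 11.11 says that the interaction sample size "would be four times that of a main effect of the same magnitude for a repeated measures outcome", and 86 × 4 = 344. The inputs are coherent, but the check is circular and does not independently verify the 80%.

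The splits 0.005/2 = 0.0025 and 0.048/2 = 0.024 are exact. The pair 0.005 and 0.048 at half information gives an overall two-sided level of 0.0499, so type I error is in order.

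**2. Smallest interaction that can cross**

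SE at 344 = 0.811 × √2 = 1.147. Threshold = 3.023 × 1.147 = 3.47 points, which is 39% above 2.5.

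**3. Behavior given crossing, true interaction 2.5**

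- Distance to the boundary: 3.023 − 2.5/1.147 = 0.843.
- P(cross) = 1 − Φ(0.843) = 0.200.
- Mean estimate = 2.5 + 1.147 × φ(0.843)/0.1995 = 2.5 + 1.61 = 4.11, or +64%.
- Ordinary 95% CI coverage = [Φ(1.96) − Φ(0.843)] / 0.1995 = (0.9750 − 0.8005)/0.1995 = 87.5%.
- Repeated CI (±3.023 SE) coverage = [Φ(3.023) − Φ(0.843)] / 0.1995 = 99.4%.

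For a true 1.25, P(cross) is 2.7% and the mean is 3.90. Coverage is 6% for the ordinary interval and 95% for the repeated one.

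**4. Marker-negative effect**

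The 1.61-point bias divides in proportion to subgroup variance, so the marker-negative share equals the marker-positive prevalence. At 50% it is 1.61/2 = 0.80 points; at 49% it is 0.79. The marker-negative SE at 344 is 1.147/√2 = 0.81, so the shift is about one SE. By simulation, the ordinary 95% CI for this effect covers about 89% given a stop on a true 2.5.

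**5. Sensitivity of the conditional figure**

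| Case | P(cross) | Mean | Overstatement |
|---|---|---|---|
| Base case | 20% | 4.11 | +64% |
| Threshold 0.005 (minimum 3.22) | 26.5% | 3.92 | +57% |
| True interaction 2.0 | 10% | 4.01 | +101% |
| True interaction 3.0 | 34% | 4.23 | +41% |
| Prevalence 30% or 70%, SD held at 5.32 | 15% | 4.43 | +77% |

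**6. All trials together**

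For a single test with a true 2.5, the bias averaged over stopping and continuing is about +6% (about −8% in trials that continue). Ordinary coverage is about 95%.

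**The case against.** **What stands.** Overestimation after an early stop affects any efficacy boundary. Controlling type I error while reporting the model estimate is a recognised choice, so this is a gap in reporting rules and not an error peculiar to this plan. The stop is advisory. The base figures are also per test. If both true interactions are 2.5, the ordered rule triggers in about 28% to 36% of trials (assumed correlation between the tests 0.8 to 0). A named interaction, averaged over all those stops, is then overstated by 29% to 52%. The dataset at a stop may exceed 344, because no enrolment pause is stated; with an assumed 20 to 60 extra children the overstatement is about 55% to 61%.

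**What a reader might infer but the documents do not support.** One reading is that the plan commits itself to reporting an unadjusted estimate after a stop. It does not say so: it is silent, and GEE is simply the only estimator named. Section 9.6 refers to an interim and final analysis plan that the DSMB reviews, and section 11.7.1 points to a Section 6.8 that this document does not contain, so a rule may exist elsewhere. Another reading is that the trial as a whole is badly biased; the +6% average says otherwise.

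**A tempting remedy that fails.** A conditional bias-corrected estimate, found by solving for the true value whose mean given crossing equals the observed one, returns 2.5 when 4.11 is observed. Near the boundary it breaks down: an observed 3.7 becomes −1.7, and 3.5 becomes −36 on a 0–40 scale. With a true 2.5, about 35% of stops would show a reversed sign, and the median absolute error rises from 1.47 to about 1.9. Conclusions should not rest on it.

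**Conclusion.** The concern holds in a limited form. The plan protects type I error at the interim but specifies no interval or caution suited to a trial that stops there. If a test on a true 2.5-point interaction triggers the stop, its estimate averages 4.11, its ordinary 95% interval covers 87.5%, and the marker-negative benefit is understated by about 0.8 points.

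These figures assume the SE back-solved from the stated 80% power, half the information at 344, the 0.0025 threshold and, for the subgroup shift, an even split. They describe a conditional event of about 20% per test. They do not show that the final analysis at 688 is unsound. The gap is still worth closing, because after an early stop these would be the estimates used to judge which children benefit.

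**What to change.** Add to section 11.6.2, before the interim data are seen:

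> If the trial stops at the interim analysis, each interaction will be reported as the GEE estimate with a repeated confidence interval based on the boundary critical value (3.02 SE for the 0.0025 level), with a statement that estimates after an early stop tend to be too large. Treatment effects in marker-negative children will be shown with an equally widened interval, labelled supportive because no boundary is defined for them. No claim of lack of benefit will rest on the ordinary interval alone.

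As an illustration, an observed 4.11 would carry 4.11 ± 3.023 × 1.147, or about 0.6 to 7.6, in place of the ordinary 1.9 to 6.4.

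The text should also say how an interaction declared significant only at the second ordered level (0.005, critical value 2.81) will be presented, since its 3.02 SE interval can include zero.

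The cost is a few lines of text and a wider, conservative interval, used only after an early stop. Sample size, boundaries and the analysis at 688 are unchanged.
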